# **Study Treatment Group 1:**

Study subjects in Group 1 will undergo Descemetorhexis without Endothelial Keratoplasty (DWEK/DSO) on Study Day 0 and will not receive any TTHX1114. Subjects in this group will function as a control arm and following DWEK/DSO will be seen in follow-up on:

- Day 1
- Day 14
- Day 28
- Day 56

Assessments conducted at follow-up visits will include routine ocular assessments.

# **Study Treatment Group 2:**

Approximately 48 to 72 hours prior to DWEK/DSO (Day -3), study subjects will receive a "conditioning dose" (10ng [10mcL]) of TTHX1114. The conditioning dose is intended to provide anti-apoptotic protection for the existing cells. On Day 0, subjects will undergo DWEK/DSO and will receive TTHX1114 (50ng [50mcL]) at the time of the surgical procedure. As described above, the immediate post-surgical anterior chamber should easily accommodate the additional volume.

Study subjects will then return for follow-up on Day 1 (the day after DWEK/DSO) and subsequent study treatment administration on:

- Day 7
- Day 14
- Day 21

Follow-up visits will occur on:

Clinical Study Protocol TTHX-002

Confidential and Proprietary

Amendment 7.0: September 22, 2022

- Day 28
- Day 56

# **Study Treatment Group 3:**

On Day 0, subjects will undergo DWEK/ DSO and will receive TTHX1114 (100ng [100mcL]) at the time of the surgical procedure. As described above, the immediate post-surgical anterior chamber should easily accommodate the additional volume.

Study subjects will then return for follow-up on Day 1 (the day after DSO) and subsequent follow-up visits will occur on:

- Day 7
- Day 14
- Day 21
- Day 28
- Day 56

#### **Study Treatment Group 4:**

On Day 0, subjects will undergo DWEK/ DSO and will receive TTHX1114 (100ng [100mcL]) at the time of the surgical procedure and then weekly injections x 3. Subjects who have not sufficiently recovered by Day 28, may receive an additional dose of TTHX1114 following discussion with the Medical Monitor.

Study subjects will then return for follow-up on Day 1 (the day after DWEK/DSO) and subsequent study treatment administration on:

- Day 7
- Day 14
- Day 21

Follow-up visits will occur on:

- Day 28\*
- Day 56

\* Subjects who have not sufficiently recovered by Day 28, may receive an additional dose of TTHX1114 following discussion with the Medical Monitor. In this context, Medical Monitor refers to Sponsor (or designee). If the Sponsor (or designee) agrees that the study subject can receive the 5th TTHX1114 administration, all assessments scheduled for Day 21 should be repeated on Day 28 and an unscheduled visit conducted on or around Day 35 when all assessments scheduled for Day 28 should be conducted.

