Images at Screening	Specular Microscopy (incl peripheral	QE.						SE	SE	SE		SE
Pentacam	images at Screening)	SE										
SE   SE   SE   SE   SE   SE   SE   SE	Assessment of Corneal Thickness b		SE		SE	SE	SE	SE	SE	SE	SE	SE
Intraocular Pressure (IOP) measurement	Pentacam		SE					SE	SE			
Pre-injection/procedure	Best-corrected Visual Acuity	SE	SE			SE	SE	SE	SE	SE	SE	SE
Post-injection   SE	Intraocular Pressure (IOP) measurement	SE		SE				SE	SE			
Urine pregnancy test (WOCBP)   X	Pre-injection/procedure		SE		SE	SE	SE					
Clinical Laboratory Collection (Chemistry, Hematology, UA, & HbA1e)  Plasma for ADA  Pre-injection  Plasma for Pharmacokinetics (PK)  Pre-injection  1.5 hours after injection  Optional Blood for Genetic Testing  V-FUCHS  X  DWEK/DSO  Collect endothelium tissue sample  Collect Aqueous Humor sample  Study Treatment IC Injection (SE)  Concomitant Medications Review  X  X  X  X  X  X  X  X  X  X  X  X  X	Post-injection c		SE		SE	SE	SE					
Clinical Laboratory Collection (Chemistry, Hematology, UA, & HbA1e)  Plasma for ADA  Pre-injection  Plasma for Pharmacokinetics (PK)  Pre-injection  1.5 hours after injection  Optional Blood for Genetic Testing  V-FUCHS  X  DWEK/DSO  Collect endothelium tissue sample  Collect Aqueous Humor sample  Study Treatment IC Injection (SE)  Concomitant Medications Review  X  X  X  X  X  X  X  X  X  X  X  X  X	Urine pregnancy test (WOCBP)	X						X				
Plasma for ADA	Clinical Laboratory Collection											
Plasma for ADA  Pre-injection  Plasma for Pharmacokinetics (PK)  Pre-injection  1.5 hours after injection  V-FUCHS  V-FUCHS  DWEK/DSO  Collect endothelium tissue sample  Collect Aqueous Humor sample  Study Treatment IC Injection (SE)  Concomitant Medications Review  X  X  X  X  X  X  X  X  X  X  X  X  X	(Chemistry, Hematology, UA, &							X				
Pre-injection	HbA1c)											
Plasma for Pharmacokinetics (PK) Pre-injection  1.5 hours after injection  Optional Blood for Genetic Testing  V-FUCHS  V-FUCHS  X  DWEK/DSO  Collect endothelium tissue sample  Collect Aqueous Humor sample  Study Treatment IC Injection (SE)  Concomitant Medications Review  X  X  X  X  X  X  X  X  X  X  X  X  X	Plasma for ADA		X					X				X
Pre-injection	Pre-injection											
1.5 hours after injection         X         Image: Concomitant Medications Review         X	Plasma for Pharmacokinetics (PK)							X				
Optional Blood for Genetic Testing         X	Pre-injection		X									

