V-FUCHS         X         X         X         X           DWEK/DSO         X         X         X         X           Collect endothelium tissue sample         X         X         X           Collect Aqueous Humor sample         X         X         X           Study Treatment IC Injection (SE)         100	1.5 hours after injection		X									
DWEK/DSO         X         Image: Collect endothelium tissue sample         Image: Collect endothelium tissue sample         X         Image: Collect endothelium tissue sample         Image: Collect endothelium tissue sample         X         Image: Collect endothelium tissue sample         Image: Collect endothelium tissue	Optional Blood for Genetic Testing		X									
Collect endothelium tissue sample         X	V-FUCHS	X						X	X			
Collect Aqueous Humor sample         X         Image: Control of the c	DWEK/DSO		X									
Study Treatment IC Injection (SE)         100 ng ng ng ng         50 ng ng ng         50 ng         <	Collect endothelium tissue sample		X									
Study Treatment IC Injection (SE)  ng  ng  ng  ng  ng  ng  ng  ng  ng  n	Collect Aqueous Humor sample		X									
Concomitant Medications Review X X X X X X X X X X X X	•		100		50	50	50					
Concomitant Medications Review X X X X X X X X X	Study Treatment IC Injection (SE)		ng		ng	ng	ng					
Assess Adverse Events X X X X X X X X	Concomitant Medications Review	X		X	X	X		X	X			
	Assess Adverse Events		X	X	X	X	X	X	X			

OU=both eyes, SE=Study Eye, V-FUCHS=Visual Function and Corneal Health Status

Note: Unless otherwise specified assessments to be performed prior to study treatment injection, if applicable \*Day 0 pre-treatment ocular assessments may be obtained within the 7 days prior to Day 0 (if screening visit assessments were within 7 days, they do not need to be repeated)

<sup>a as part of Comprehensive Eye Examination

<sup>b measured by AS-OCT (preferred) if AS-OCT not available, Pentacam or Ultrasound Pachymetry is to be used (Note: subjects must be assessed using the same modality throughout the study)

<sup>c IOP pre-injection and then post-injection every 30 to 60 minutes until less than at least 5 mmHg higher than pre-injection IOP (Note: IOP may not be measurable post injection on Day 0)

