\*End of Study Visit (EOS) may be performed any time after Day 168; if the Day 336 visit, if the subject has already completed the study, the subject should be contacted and asked to provide a plasma sample for ADA; any subject who did not have gradeable specular images at their most recent visit should be re-imaged and gradeable images obtained

Confidential and Proprietary

Amendment 7.0: September 22, 2022

Table 5: Schedule of Events Group 1a

Study TTHX-002: Group 1a											
					Study	y Day					
	0*	7	14	21	28	35	56	84	168	336	
		(±1)	(±1)	(±1)	(±1)	(±3)	(±3)	(±21)	(±21)	(±21)	
Informed Consent											
Comprehensive Ocular Examination											
(including slit lamp examination and	SE				SE	SE	SE				
dilated exam of the lens, fundus, and	SE				SE	SE	SE				
vitreous)											
Slit Lamp	SE	SE	SE	SE	SEa	SE a	SE a				
Specular Microscopy	SE		SE	SE	SE	SE	SE			SE	
Assessment of Corneal Thickness b	SE		SE	SE	SE	SE	SE	SE	SE	SE	
Best-corrected Visual Acuity	SE	SE	SE	SE	SE	SE	SE	SE	SE	SE	
Intraocular Pressure (IOP)					SE	SE	SE				
measurement											
Pre-injection/procedure	SE	SE	SE	SE	SE						
Post-injection c	SE	SE	SE	SE	SE						
Urine pregnancy test (WOCBP)	X				X						
Clinical Laboratory Collection											
(Chemistry, Hematology, UA, &					X						
HbA1c)											
Plasma for ADA	X				X						
Pre-injection											
Plasma for Pharmacokinetics (PK)					X						
V-FUCHS						X	X				
Study Treatment IC Injection (SE)	X	X	X	X	X						
Concomitant Medications Review	X	X	X	X	X	X	X				
Assess Adverse Events	X	X	X	X	X	X	X				

OU=both eyes, SE=Study Eye, V-FUCHS=Visual Function and Corneal Health Status

Note: Unless otherwise specified assessments to be performed prior to study treatment injection, if applicable

\*Day 0 pretreatment assessments may be obtained within the 7 days prior to Day 0 (if screening assessment within 7 days, do not need to be repeated)

<sup>a as part of Comprehensive Eye Examination

<sup>b measured by AS-OCT (preferred) if AS-OCT not available, Pentacam, or Ultrasound Pachymetry is to be used (Note: subjects must be assessed using the same modality throughout the study)

<sup>c IOP pre-injection and then post-injection every 30 to 60 minutes until less than at least 5 mmHg higher than pre-injection IOP

Confidential and Proprietary

Amendment 7.0: September 22, 2022

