### 6.4.6 Specular Microscopy

Specular microscopy images will be obtained of the periphery and center of the cornea. The center of the cornea is defined as the region of the cornea above the pupil. If a subject is to be dilated at a visit, specular microscopy should be performed prior to dilation. To address differences in location of the image within a given area of the cornea, five acceptable images should be taken at each required timepoint. Peripheral images will be collected at the screening visit; central images will be collected at prior to treatment and whenever possible following treatment. Due to the nature of corneal edema following DSO, specular microscopy images may not be able to be obtained at all post-operative timepoint prior the deturgescence of the cornea. Attempts should be made to collect images at all timepoints; if images are unable to be obtained, the reason for not being able to collect images will be recorded. If specular microscopy images are obtainable, it is expected that images will remain obtainable at all subsequent timepoints. Prior to the end of each specular microscopy session, the technician should review the images to ensure that the captured images are of the highest quality obtainable. Subjects with inadequate images may be required to return to the investigational site for repeat imaging as an unscheduled visit.

Endothelial cell density, percent hexagonality and the coefficient of variation will be assessed from specular microscope images.

Cornea Image Analysis Reading Center (CIARC) at University Hospitals Cleveland Medical Center will function as the centralized reading center and will be responsible for the certification of equipment and training of technicians as well as reading images and conducting image analysis. If more than one specular microscope is installed at a site, the same specular microscope will be used for all visits for a given patient.

Clinical Study Protocol TTHX-002

[figure not shown]
Trefoil Therapeutics, Inc.

Confidential and Proprietary

[figure not shown]
Amendment 7.0: September 22, 2022

Baseline images and on-study central images will be sent to CIARC; baseline images will be archived, and on-study images will be assessed for efficacy.

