#### 7. ASSESSMENT OF EFFICACY

As described above, the efficacy endpoints will be visual acuity and endothelial cell count/density as measures by specular microscopy. Other efficacy assessments include:

- Slit lamp biomicroscopy assessments
- Central corneal thickness
- IOP

The primary efficacy timepoint is Day 28.

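### On the natural reading of section 4, Group 4 eyes given a fifth dose have no required post-operative cell count or V-FUCHS before that dose, although Day 28 is the primary timepoint

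*Combined protocol and SAP*

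**What the plan says.** Section 4, under Study Treatment Group 4, allows one further injection for subjects whose recovery by Day 28 is judged insufficient, if the sponsor or its designee agrees. Two instructions then apply: "all assessments scheduled for Day 21 should be repeated on Day 28", and there is to be "an unscheduled visit conducted on or around Day 35 when all assessments scheduled for Day 28 should be conducted".

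Table 4 defines what each of those sets contains. Specular microscopy is marked at Screening and on Days 28, 56, 84 and 336. V-FUCHS is marked at Screening and on Days 28 and 56. Neither is marked on Day 21. BCVA and corneal thickness are marked on both Day 21 and Day 28. The note to the table adds: "Unless otherwise specified assessments to be performed prior to study treatment injection, if applicable".

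Section 7 says that "the efficacy endpoints will be visual acuity and endothelial cell count/density as measures by specular microscopy" and that "The primary efficacy timepoint is Day 28". Section 3 also places cell counts within the primary efficacy endpoint. Section 4.1 ties two measures to Day 28 by name, the count of subjects at 20/40 or better and central corneal thickness. Its list of additional endpoints is not shown in the public copy.

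Two general sections also bear on this. Section 6.4.6 asks for specular images to be attempted at every timepoint, accepts that oedema may prevent them, and provides that "if images are unable to be obtained, the reason for not being able to collect images will be recorded". Section 6.4.11 calls for extra ocular assessments in delayed recovery, at Day 28 among other times. Its list of options includes Pentacam but does not name specular microscopy.

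**The concern.** The fifth dose is given because of outcome: only eyes that are healing slowly receive it. If the same decision also shifts the cell count and the questionnaire to a week after the dose, the Day 28 data are incomplete in exactly the eyes with the poorest early course. A Day 28 cell-count summary for Group 4 then has two choices. It can omit these eyes, or it can mix four-dose values at Day 28 with five-dose values at about Day 35. Either choice could flatter Group 4 beside Group 3, where Table 3 schedules specular microscopy and V-FUCHS on Day 28 for every eye. The loss cannot be repaired at the analysis stage, because a pre-dose image that was never taken cannot be recovered.

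**Working it through.** The plan states no figure on this point, so the check compares the columns of Table 4 and applies the section 4 rule to them.

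**Step 1. What moves.** For a fifth-dose eye the rule gives: Day 28 visit = Day 21 column; visit at about Day 35 = Day 28 column.

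| Assessment (Table 4) | Day 21 column | Day 28 column | Fifth-dose eye, required on Day 28 |
|---|---|---|---|
| BCVA | yes | yes | yes |
| Corneal thickness | yes | yes | yes |
| Slit lamp | yes | yes | yes |
| IOP | before and after injection | yes | before and after injection |
| Specular microscopy | no | yes | no |
| V-FUCHS | no | yes | no |
| Pentacam | no | yes | no (optional under 6.4.11) |
| Comprehensive examination | no | yes | no |
| Pregnancy test, laboratory, ADA, PK | no | yes | no |

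**Step 2. Order relative to dose five.** Scheduled post-operative specular visits are Days 28, 56, 84 and 336, four in all. For a fifth-dose eye they become about Day 35 and Days 56, 84 and 336. The number before dose five is 0 of 4, and the last required image before that dose is the one at Screening, before surgery.

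**Step 3. Timing.** Day 35 is 35 − 28 = 7 days after dose five. Time since surgery is 35/28 = 1.25, or 25% longer. The Day 28 window is ±3 days, so Day 35 lies 35 − (28 + 3) = 4 days beyond it. The window does not formally govern an unscheduled visit, but the gap shows that the value is not a Day 28 value.

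**Step 4. Move or addition?** The rule has the Day 21 set repeated on Day 28, but speaks of the Day 28 set as conducted, not repeated, at about Day 35. If the full Day 28 set also stayed on Day 28, repeating the Day 21 set would add little beyond the injection and its IOP checks. The wording therefore favours a move, but nothing in section 4 or Table 4 states that the Day 28 column is cancelled.

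**Step 5. Does an injection day prevent imaging?** No. Table 5 gives Group 1a an injection on Day 28 and schedules specular microscopy and the comprehensive examination on that day and again on Day 35. It schedules V-FUCHS on Days 35 and 56 only, so it is a precedent for the imaging and not for the questionnaire.

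**Step 6. Size.** Table 7 plans 20 subjects in Group 4, so each fifth-dose subject is 1/20 = 5%. The number of fifth doses is not stated. Under assumed counts: 2/20 = 10%, 5/20 = 25%, 10/20 = 50%. For specular data these are upper limits on what a fix could recover, because oedema will prevent some images.

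**The case against.** The strongest reply is that the rule may be additive. The ordinary Day 28 visit could be where insufficient recovery is judged, with the Day 21 set repeated on top to cover the injection and its IOP checks. A site working that way would already hold a pre-dose image. This stands as a possible reading. It does not remove the point, because the plan does not require that sequence and sites can reasonably differ.

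A second reply is that the general sections cover the gap. Section 6.4.11 does mean that Pentacam may already be done on Day 28 in these eyes. It does not name specular microscopy or V-FUCHS, and its individual tests are optional. The request in section 6.4.6 for attempts at all timepoints does not make Day 28 a specular timepoint when the Day 21 set is the one in force.

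Third, the measures that section 4.1 ties to Day 28 by name are intact, and section 6.4.4 treats BCVA as the primary efficacy measurement. That is correct, and it limits the point. No visible section defines a cell-count endpoint expressly at Day 28; the link comes from reading the two statements in section 7 together, with section 3. V-FUCHS appears in no visible endpoint list.

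Fourth, these are the eyes in which oedema is most likely to defeat imaging. That is also fair. The gain is that a failed attempt at a required timepoint leaves a recorded reason, whereas an image that was never scheduled leaves none.

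**Conclusion.** The point holds as a limited gap with a cheap remedy. On the natural reading of the Group 4 rule, fifth-dose eyes have no required post-operative specular microscopy or V-FUCHS before dose five (0 of 4 specular visits), and the first such data come about 7 days after it. Each affected subject is 5% of planned Group 4. The total is unknown, and the 10% to 50% range rests on assumed counts.

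A reader might infer more than the documents support:

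- **That the 20/40 count or corneal thickness is biased.** Both are in the Day 21 set and so are still measured on Day 28, before the injection. If those values are used, this rule adds no bias to either.
- **That Day 28 imaging is ruled out.** Section 4 neither forbids it nor cancels the Table 4 column.
- **That Day 35 values will be reported as Day 28.** The later visit is called unscheduled, and actual dates are recorded under sections 6.4 and 6.5.5. The full SAP is to be written before database lock (section 9.3), so its visit rules cannot be faulted unseen.
- **That these eyes leave the Per Protocol Set.** Table 12 requires sufficient endpoint data but does not say that a missing image alone fails that test.

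**What to change.** 1. In section 4 (Study Treatment Group 4) and a footnote to Table 4, state: *On Day 28, before any fifth injection, complete V-FUCHS, BCVA, corneal thickness and specular microscopy (attempted, and before any dilation). Repeat these at about Day 35.* IOP before and after the injection is already part of the repeated Day 21 set. This also settles whether the rule moves these assessments or adds to them.
2. Leave the pregnancy test, clinical laboratory, ADA and PK samples at about Day 35. That keeps the same gap after the last dose as in a four-dose eye (28 − 21 = 7 days; 35 − 28 = 7 days), and section 6.4.10 wants the pregnancy test once treatment is complete.
3. In the SAP, let only Day 28 pre-dose values feed Day 28 endpoints. Label the later visit Day 35 and summarise it separately. Where a Day 28 image cannot be obtained, leave the value missing, with the reason recorded as section 6.4.6 already provides.

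The cost is a wording change, one footnote and one SAP rule. Fifth-dose subjects have specular microscopy and V-FUCHS once more, at a visit they already attend. The downside is a slightly longer Day 28 injection visit, and some images will still not be obtainable. For eyes already dosed, only the labelling rule in item 3 can help.

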# **Study Treatment Group 1a:**

TTHX1114-naive subjects in Group 1 may be allowed to "roll-over" to a TTHX1114 regimen of up to 5 weekly injections of TTHX1114. To be eligible for Group 1a, subjects must

Amendment 7.0: September 22, 2022

- continue to be eligible for the study (e.g., have a suitable fellow eye and not have had any severe suspected adverse reactions)
- not have achieved adequate restoration of the endothelium (anatomic recovery) by the anticipated timepoint following the DWEK/DSO procedure (e.g., Day 56 or 84)
  - Note: the trigger for roll over to Group 1a may be earlier if the time to anatomic recovery observed in Group 2 or 3 is sooner

Subjects who had previously participated in Group 1 will receive up to 5 weekly study treatment administrations.

- Day 0
- Day 7
- Day 14
- Day 21
- Day 28

Follow-up visits will occur on:

- Day 35
- Day 56

# **Study Treatment Group 3a:**

Subjects in Group 3 may be allowed to "roll-over" to a TTHX1114 regimen of up to 4 weekly injections of TTHX1114. To be eligible for Group 3a, subjects must

- continue to be eligible for the study (e.g., have a suitable fellow eye and not have had any severe suspected adverse reactions)
- not have achieved adequate restoration of the endothelium (anatomic recovery) by the anticipated timepoint following the DWEK/DSO procedure (e.g., Day 56 or 84)
  - Note: the trigger for roll over to Group 3a may be earlier if the time to anatomic recovery observed in Group 2 or 3 is sooner

Subjects who had previous participated in Group 3 will receive up to 4 weekly study treatment administrations.

- Day 0
- Day 7
- Day 14
- Day 21

Follow-up visits will occur on:

- Day 28
- Day 56

#### **Long-term Follow-up (All Treatment Groups)**

A subjects will undergo long-term follow-up for up to 1 year following the later of DWEK/DSO or the first TTHX1114 administration.

Amendment 7.0: September 22, 2022

- Long-term Follow-up visits will occur on: Day 84
- Day 168
- Day 336/ End of Study Visit

For subjects who have had both eyes treated on study, the Day 168 and Day 336 visits for both eyes may be combined calculated based on the date of surgery of the second eye. Day 336 is considered the End of Study Visit and includes a Comprehensive Eye Examination.

#### **End of Study Visit**

An End of Study Visit (EOS) will be performed on all subjects. The EOS may be conducted any time after Day 168, during the EOS assessments scheduled for Day 336 will be performed and a plasma sample for ADA analysis will be collected. If the subject has already completed the study, the subjects should be contacted and asked to provide a plasma sample for ADA. Any subject who did not have gradeable specular images at their most recent visit should be reimaged and gradable images obtained. It is important that gradeable specular images are collected for all subjects at the subjects' last visit.

